**INSTRUCTIONS**

This template is intended to help investigators prepare a protocol that includes all of the necessary information needed by the IRB to determine whether a study meets approval criteria. **Read the following instructions before proceeding:**

1. Use this protocol template for a PI initiated study that includes direct interactions with research subjects. Additional templates for other types of research protocols are available in the system Library:
  - If the study involves genetic testing, blood draws, or MRIs, do not use this form. Use the [biomedical protocol template](#).
  - If the study involves secondary analysis of data, use [the Secondary Analysis of Data protocol](#).
  - For activities that may qualify as exempt research, use [the Request for Exemption form](#) (which includes a decision tree to determine whether or not your study qualifies as exempt).
2. If a section or question does not apply to your research study, type “Not Applicable” underneath.
3. Once completed, upload your protocol in the “Basic Information” screen in IRES IRB system.

## SECTION I: GENERAL INFORMATION

1. **Probable Duration of Project:** State the expected duration of the project, including all follow-up and data analysis activities.

The project was launched on July 24th, 2020, with a pilot of the intervention in 10 villages. The main trial is expected to start on September 23rd and last 12 weeks. An initial participant phone survey will begin on September 23rd, 2020, with follow up phone surveys scheduled for the weeks of October 18th and November 16th, 2020, with the potential for longer-term follow-up surveys. Throughout the 12 weeks of the study duration (September 23rd – December 12th), we will conduct mask distribution and promotion as well as field observations of participants behavior in complying with different COVID-19 mitigation strategies. We expect to complete all data analysis for the project during the month of November. Given the urgent need to provide timely public health recommendations in light of the COVID-19 pandemic, this project will operate under a shorter duration than usual.

2. **Study location:** State where the study will take place and in what setting.

Bangladesh

If international, complete and submit **International checklist** (<http://your.yale.edu/policies-procedures/forms/450-ch-1-international-research-checklist>) Note: If your research involves interactions with any embargoed countries you should contact the Director of Corporate Contracts and Export Control Licensing ([[contact]](mailto:[contact]) or call [contact]) for guidance on how to proceed.

3. **Help us categorize your research.** Are you using any of the following?

- Class Project
- Participant Observation
- Interviews
- Surveys
- Focus groups (study is not anonymous)
- Research in K-12 schools (submit a School Agreement form for the study)
- Deception (submit a Debriefing sheet)
- Audiotaping, videotaping or photography of individuals (study is not anonymous)
- Public viewing of videotapes or photographs
- Yale Psychology Pool (study does not qualify for exemption)
- International research sites (attach the International Checklist)
- Online (web-based) activities
- Social networks

#### SECTION IV: RESEARCH PLAN

1. **Statement of Purpose:** State the scientific aim(s) of the study, or the hypotheses to be tested.

This study aims to measure the benefits of facemasks in preventing transmission of respiratory infections (especially COVID-19) and to study how different enforcement mechanisms can be used to increase mask use. In particular, this study has six main aims:

1. To develop a scalable intervention that can increase consistent use of a quality mask
2. To assess the impact of appropriately used high-quality masks on the transmission of COVID-19
3. To assess the effect of mask-wearing in reducing the wearer's risk of infection with COVID-19
4. To assess the effectiveness of high-quality cloth vs. "surgical" masks in reducing the spread of COVID-19
5. To evaluate whether increased mask use is associated with risk compensation (an increase in leaving the home or reduced compensation)
6. To assess the protective effect of masks with high filtration and breathability relative to existing face-coverings

We believe that a successful study could influence decision-makers through several channels:

- Our intervention would evaluate whether mask distribution combined with consistent messaging is sufficient to create norms of mask use in places where current mask use is low. Context-appropriate variations of the program we design to increase mask take-up could be replicated in other Asian and African countries with similar implementation and enforcement challenges as Bangladesh.
- Most people in the world still live in countries that do not mandate mask use despite community spread of COVID-19, and mandates may not go far enough. Direct evidence that masks reduce transmission of the virus would strengthen the hand of those pushing for action in those countries.
- Direct evidence of this type would shift the priorities of public health agencies with limited resources if masks are proven effective.
- With direct evidence of the additional protective value of scientifically-validated masks, many individuals, NGOs and governments would invest more in producing such masks.

Additionally, if successful, the intervention in the study will cost-effectively save lives. The above "theory of change" adds to this direct impact.

2. **Background:** Describe the background information that led to the plan for this project. **Provide references** to support the expectation of obtaining useful scientific data.

a) The Case for Mask Adoption

There is substantial evidence from laboratory studies that masks can reduce exhaled viral load, and all major public health organizations recommend that those with symptoms of COVID-19 wear masks for this

---

 See, for example:

reason. There is also substantial evidence of asymptomatic or presymptomatic transmission of COVID-19. This suggests that universal adoption of cloth masks (if used regularly and properly) – including by those who appear healthy – may substantially reduce the transmission rate of the virus.

However, to date, there are few estimates of the degree to which mask adoption actually reduces *transmission* of the virus in the field. Non-experimental estimates suggest that masks lower transmission by 40-50%.

b) Current Situation

Take-up of masks is highly variable across countries, ranging from 0-20% in the UK, Norway, Finland and Denmark to close to 100% in several Asian countries with historic norms of mask use. As of July 5th, 2020, 4.3 billion people live in countries that do not formally mandate mask use, and 240 million live in countries where mask use is not recommended in any way.

The relationship between mask requirements and mask take-up can be complex, especially in the developing world. In Bangladesh, the government has strongly recommended mask use since early April. This policy was initially accompanied by consistent public messaging, as well as attempts by police and NGOs to confront those who were seen in public without masks. Our surveys from this period indicate that

---

throughout Bangladesh, compliance was high, with 80-95% of respondents reporting that they wore masks in public areas.

Our more recent data, as well as our conversations with officials, suggests that this trend has now reversed. The Bangladeshi government formally mandated mask use in late May and began fining non-compliers; nonetheless, in our latest survey of mask use, we observed 100,000 people in public areas throughout Bangladesh and found that only 26% were wearing masks despite the severity of the epidemic continuing to increase.

3. **Research Plan:** Summarize the study design and research procedures using non-technical language that can be readily understood by someone outside the discipline. If working with a Non-Government Organization (NGO) or other organization, be sure to highlight which are research-only activities and which activities would occur regardless of the research. If working with survey firms, please specify what research activities the research firm will be responsible for.

We have four main research questions we seek to answer:

1. Can mask distribution and promotion at mosques, markets, and homes successfully change community mask-wearing norms from the status quo to appropriate wearing of high-quality masks?
2. Can community mask-wearing reduce the transmission of symptomatic respiratory infections and symptomatic COVID-19 infection?
3. Does mask-wearing induce risk-compensation such as an increase in leaving the home or reduced physical distancing?
4. Can mask-wearing reduce the risk of COVID-19 infection for the individual mask wearer?

To answer the first three questions, we will randomize an intervention package at the level of markets and associated villages.

To answer the fourth question, we will randomly choose a small fraction of high-risk individuals in control regions and provide them masks and instructions for proper mask use to assess whether masks protect against infection.

#### Village-level experiment (Research Questions 1, 2 and 3)

#### *Study Design*

We will start by identifying 700 markets, along with the most centrally located village and the mosque attended by most residents of that village. We expect this to comprise about 250 households, or 500 adults per village. We will call this entity a “market+” (plural: markets+).

In order to evaluate whether masks prevent the spread of COVID by preventing transmission and/or protecting the wearer, we will randomize markets+ into treatment and control groups. Our intervention will involve distributing masks at no cost at mosques, markets and directly at people’s homes. We will combine the mask distribution with appropriate behavior change communication and messaging involving imams, market committee leadership and community leaders. We will stratify on markets+ within the same upazila, keeping all markets+ at least 5-10 km apart to minimize spillovers.

Half of the 700 markets+ will be assigned to the treatment group. We intend to stratify to that treatment and control groups are as balanced as possible in terms of ex ante likelihood of COVID-19 infections. To do so, we will: 1) stratify by upazilas and 2) stratify by unions that have similar case rates. For “markets+” that are in the same Upazila and in unions with similar rates of cases, we will list them in order of population and do pairwise stratification by population.

[figure not shown]

Figure 1: Village-level experiment study design

### *Outcomes*

#### Primary outcomes:

1. Symptomatic SARS-COV2 Infection assessed at 12 weeks via serological testing

#### Secondary outcomes:

1. The impact of the intervention on mask use in mosques, markets and other public areas, including the fraction a) appropriately (covering the nose and chin) wearing a mask distributed by our project, b) appropriately wearing a mask that was not distributed by our project, c) inappropriately wearing any a mask or other face covering, or d) are not wearing a face covering at all, and also the fraction specifically wearing our distinctive mask.
2. Prevalence of symptoms of respiratory infection among all individuals for whom we collect phone numbers
3. The prevalence of symptoms of respiratory infection, disaggregated by market vendors, market-goers, imams, mosque-workers, and mosque-goers and none of the above.
4. Number and fraction of pharmacy customers that purchase medicines for symptoms of respiratory infections.
5. Physical distancing behavior measured by direct observation of behavior in mosques.
6. Percentage of adults out of their homes and visiting tea stalls and mosques.
7. Any available data (likely incomplete) on hospitalizations and COVID-19 mortality in each community. This data will be aggregate data which is de-identified from local hospitals and clinics. We expect this data to be sparse and incomplete.
8. Effectiveness of pre-intervention masks by examining the effect size of the intervention with respect to the percent of mask-wearing prior to the intervention. For example, the intervention may increase mask use to 30% in both different treatment villages. If the effect of the intervention on COVID-19 infection rate is the same in villages where people 0% of people were wearing face coverings pre-intervention and where 50% of people were wearing face coverings pre-intervention, this would suggest that the type of face coverings worn prior to the intervention were ineffective.

This analysis uses the variation generated by the randomization but also requires additional assumptions since the baseline rate of mask use is not randomized.

*Intervention activities*

In the treatment arm we will conduct the following intervention activities for four weeks:

- Role modeling
  - Ask imams, public officials and community leaders to commit to wearing masks whenever they leave the house, including while imams deliver prayer at the mosque. It's important to get all influential role-models engaged with our intervention.
- Communities and households:
  - We will encourage local community leaders to endorse a statement mandating that everyone wear masks
  - Community mask promoters will go door to door to each household in the market+ and distribute up to 2 masks to each household (one for each household member) and discuss the value of wearing masks in public. During these household visits our surveyors will wear masks and maintain physical distance whenever possible; they will also cleanse their hands with hand sanitizer between each household visit. This will occur immediately after our baseline survey.
- At mosques:
  - Distribute one mask to each worshipper as he enters the mosque for Jummah prayer each Friday.
  - Provide imams with behavior change communication to encourage regular and appropriate mask use in public areas, both in the mosque and elsewhere. Imams will variously appeal to men as guardians of their family's health, men as individuals who want to stay healthy so they can continue working, as respected business owners and leaders in the community, and as business owners who want to continue to keep their businesses open. They will also reinforce that men should share the messages about the importance of wearing masks with their families in order to help keep them safe.
  - Hand out a visual brochure produced by the World Health Organization (WHO) that underscores the value of mask wearing and shows how to properly wear and clean a mask.
- At markets:
  - Speak to the committee of shop owners at each treated market, explain the importance of mask use, and ask them to commit to wearing masks, as well as directing the market vendors to wear a mask at all times.
  - Every other day, distribute one mask to each person who visits the markets and hire one mask promoter to encourage all people at the market to wear masks by emphasizing the individual's duty and ability to keep their community safe
  - Have an agreement with the officials managing the market to also encourage people to wear masks on days when our monitors are not present
  - Hand out the aforementioned brochure on the masks
  - An audio recording reminding people to please wear masks will play at markets periodically

Control groups will not be included in mask distribution or mask promotion. We will distribute masks that are manufactured specifically for this project and have a distinctive color and design, so that our enumerators can directly observe whether people are wearing the distributed masks or other masks.

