#### Appropriate mask use

- Count the number of mosque-goers (every Friday), market-goers (one day per week), and people in public near the village entrance, indoor restaurants as people enter or exit who are a) appropriately (covering the nose and chin) wearing a mask distributed by our project, b) appropriately wearing a mask that was not distributed by our project, c) inappropriately wearing any a mask or other face covering, or d) are not wearing a face covering at all, and also the fraction specifically wearing our distinctive mask.

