## Physical distancing

- Conduct observations to assess physical distancing using the same criteria as the above “markets+” experiment

Mask Production, Distribution, and Promotion

Villages in the treatment arm will be randomized to receive cloth masks or surgical masks. The Standard Group, one of the largest manufacturers of ready-made garments in Bangladesh and part of the Bangladesh Garment Manufacturers and Exporters Association (BGMEA) is prepared to produce 400,000+ cloth masks according to our specifications.

After an extensive review of the literature on fabrics for low-cost masks and testing at Stanford University, we have selected to use a mask that has outer layer of 100% non-woven polypropylene, a middle layer of 60% cotton/40% polyester interlocking knit, and an inner layer made of the same interlocking knit, and an inner layer made of the same interlocking knit. The fabric will be sewn into a mask with a flat front panel that bunches near the ears and is affixed to the head with ear straps and a metal wire nose brace. The mask fully covers the nose and mouth even with animated talking. The mask is comfortable, partially because it does not hold hot air over the face. We estimate this mask is approximately 60% efficient at blocking particles 300 nm in size at a flow velocity of 10 cm/s (the particle size and approximate flow velocity specified by the U.S. National Institute of Occupational Safety and Health). This compares to bandanas that are <10% effective at a similar flow velocity and surgical masks which have filtration efficacies ranging from 40-70%.

Surgical masks, made from outer and inner layers of spunbound material and a middle layer of meltblown material, vary in quality but generally have much higher filtration efficiency than cloth masks. Even after surgical masks have been washed 10 times, their filtration efficiency is still higher than most cloth

---

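### Secondary outcome 8: equal effects at 0% and 50% prior covering point to ineffective old coverings only if project masks displace them

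*Protocol*

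**What the plan says.** The sixth aim in the Protocol's Statement of Purpose (Section IV.1) is "To assess the protective effect of masks with high filtration and breathability relative to existing face-coverings". Item 8 of the village-level secondary outcomes (Section IV.3) addresses the coverings people already had, by "examining the effect size of the intervention with respect to the percent of mask-wearing prior to the intervention".

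The item gives an example. It supposes that "the intervention may increase mask use to 30% in both different treatment villages", and contrasts a village with no prior covering with one "where 50% of people were wearing face coverings pre-intervention". If the effect on infection is the same in both, "this would suggest that the type of face coverings worn prior to the intervention were ineffective". A closing remark says the analysis "also requires additional assumptions since the baseline rate of mask use is not randomized".

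The item does not say whether project masks replace old coverings or go to people who wore none, or on which scale the effects are to be the same. The data-collection section (Appropriate mask use) plans counts in both arms of four categories: project mask worn appropriately, "appropriately wearing a mask that was not distributed by our project", inappropriate wear of any covering, and no covering.

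**The concern.** The effect of handing out masks depends on what they replace. A project mask on a previously bare face gives its full protection. A project mask that replaces an old covering gives only the difference between the two. Equal effects in the two villages can therefore mean that old coverings do nothing, or that few old coverings were replaced. The example names only the first.

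The caveat concerns confounding: villages with high and low prior use may differ in other ways. Displacement is a separate matter and would remain if baseline use had been randomised.

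At stake is the answer to Aim 6. Coverings that work could produce the very pattern the example reads as a sign that they do not.

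**Working it through.** **Inputs from the Protocol (item 8).** Project-mask use after the intervention is m = 0.30 in both villages. Prior covering is 0 in village A and b = 0.50 in village B.

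**Assumptions.**
- e_new, protection per project-mask wearer: 0.4 to 0.6. The Protocol gives filtration, not protection against infection: "We estimate this mask is approximately 60% efficient at blocking particles 300 nm in size" (Mask Production, Distribution, and Promotion).
- e_old, protection per old-covering wearer: 0 to 0.4. The Protocol gives only a filtration figure below 10% for bandanas.
- s, the share of project-mask adopters who gave up an old covering: 0 to 1.
- r, the infection risk with no covering. Risk is taken as linear in use, r(1 − e_old·p_old − e_new·p_new), and control villages keep their prior use.

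The Protocol states no figure of its own for this analysis, so there is none to reproduce.

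**Step 1: the example's arithmetic.** From 0% to 30% is a rise of 30 points. From 50% to 30% is a fall of 20 points, not an increase. The 30% makes sense only as project-mask use.

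**Step 2: formulas.**
- Village A: absolute effect r·m·e_new; relative effect m·e_new.
- Village B: absolute effect r·m·(e_new − s·e_old); relative effect m·(e_new − s·e_old)/(1 − b·e_old).
- Gap A − B, absolute with equal r: r·m·s·e_old. This is zero for every e_old when s = 0.
- Gap A − B, relative: m·e_old·(s − b·e_new)/(1 − b·e_old). This is zero for every e_old when s = b·e_new.

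**Step 3: numbers with e_new = 0.6 and e_old = 0.3 (old coverings half as good).** Village A has 0.180r and 18.0%.

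| s | Total covering in B, b + m(1 − s) | Absolute effect in B | Relative effect in B |
|---|---|---|---|
| 0 | 80% | 0.180r (same as A) | 0.180/0.85 = 21.2% |
| 0.30 | 71% | 0.153r | 0.153/0.85 = 18.0% (same as A) |
| 0.50 | 65% | 0.135r | 0.135/0.85 = 15.9% |
| 1 | 50% | 0.090r | 0.090/0.85 = 10.6% |

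**Step 4: range.** At s = 0 the absolute effect in B stays at 0.180r for e_old of 0.1, 0.2, 0.3 and 0.4. At s = 0.30 the relative effect stays at 18.0% for the same values. With e_new = 0.4, village A has 0.120r and 12.0%. Village B matches it on the absolute scale at s = 0, and on the relative scale at s = 0.5 × 0.4 = 0.20.

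**Step 5: background risk.** Under full displacement (s = 1) with e_new = 0.6, absolute effects are still equal if r_B/r_A = e_new/(e_new − e_old). That is 1.2, 1.5 and 2.0 for e_old of 0.1, 0.2 and 0.3. In this model r cancels on the relative scale.

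**Step 6: when the example's reading is right.** With s = 1 and equal r, equality on either scale requires e_old = 0. With uptake proportional to prior use (s = b = 0.5), effects differ on both scales whenever e_old > 0.

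**The case against.** The passage is an example for the last of eight secondary outcomes. It is phrased as a suggestion and admits that further assumptions are needed. A reader might infer that the plan treats a lack of difference as proof that old coverings do not work. The text sets no test or threshold and does not say that. This stands, and it lowers the weight of the point.

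The exact equalities are special cases. Zero displacement means that every adopter came from the uncovered half, yet masks are offered to every household, worshipper and market visitor, so current wearers receive them too. Even at zero displacement the relative effects differ (18.0% against 21.2%). Under proportional or full displacement with equal background risk, the example points the right way. This also stands. It shows that the reading depends on displacement, which the item leaves unstated.

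The interaction model and its interval are usual matter for a statistical analysis plan, which is not shown. That is fair, and their absence is not the finding. The finding is an inference that the Protocol does state.

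Two stronger readings are tempting. A reader might infer that a moderate gap, such as 18.0% against 15.9%, could not be told from none. The Protocol gives no event rate, intracluster correlation or standard error for this analysis, so that cannot be said. A reader might also infer that item 8 is the only outcome bearing on Aim 6. The individual-level experiment compares vendors given project masks with controls who may wear other local coverings (Section VIII, Alternatives), and it observes mask use by the same criteria. It is not a clean comparison, but it bears on the aim.

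**Conclusion.** The point holds in limited form. Equal effects support the example's conclusion only if displacement is substantial and, on the absolute scale, background risk is equal. Otherwise coverings with real efficacy can give equal effects: on the absolute scale at no displacement, and on the relative scale at 20% to 30% displacement for project-mask efficacy of 0.4 to 0.6. The efficacy values are illustrative, but the equalities hold for any old-covering efficacy within the linear model. The caveat about non-randomised baseline use does not reach this, and the 30% against 50% example needs correcting. Severity is minor: the wording is hedged, the outcome is secondary, and the primary comparison is untouched.

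**What to change.** 1. Reword the example so that project-mask use reaches 30% in both villages.
2. State the scale, absolute or relative, on which effects are compared.
3. Add displacement and equal background risk to the named assumptions.
4. Estimate displacement as the treatment–control difference in non-project mask use, relative to project-mask use, from the counts already planned. This is approximate, because inappropriate wear pools all mask types.
5. Report the treatment-by-baseline-use interaction with its confidence interval beside the displacement estimate.
6. Conclude that old coverings are ineffective only if displacement is substantial and the interval excludes an efficacy that would be useful, with that efficacy named in advance.

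Items 1 to 3 are wording; items 4 to 6 can sit in the statistical analysis plan. No new data are needed. The cost is a small extra analysis and a more cautious conclusion on Aim 6, possibly none from this outcome if displacement proves small.

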#### SECTION V: RECRUITMENT/CONSENT AND ASSENT PROCEDURES

**1. Recruitment Procedures:**

a. Describe how potential participants will be identified and contacted, and by whom.

- At participating mosques, worshippers will be given masks as they enter mosques for Friday Jumuah prayer in the treatment arm, as well as brochures with public health guidelines and recommendations as they exit the mosques. This will be conducted by members of the IPA Bangladesh team. Imams or mosque officials will also communicate with their community members to encourage compliance with the study's public health guidelines.
- At participating markets, we will reach vendors and market-goers as they enter each market in the treatment arm and receive masks handed out by members of the IPA Bangladesh team. We will also hire monitors who will go around each market throughout the study period to encourage people to wear masks.
- In public areas including tea stalls and factories, we will provide individuals with masks handed out by members of the IPA Bangladesh team.
- At participating indoor markets, we will reach vendors at their stalls and provide them with masks handed out by members of the IPA Bangladesh team.
- At participating villages, we will conduct visits inside communities to hand out masks to individual community members.

Are you collecting any information about the individuals prior to their signing a consent form?

Yes  No

If yes, indicate what information you will be collecting and how it will be gathered (*phone screen, paper questionnaire, etc.*) [Click or tap here to enter text.](#)

**2. Indicate recruitment methods below.** Attach copies of any recruitment materials that will be used.

 Flyers	 Internet/web postings	 Radio
 Posters	 Mass email solicitation	 Telephone
 Letter	 Departmental/Center website	 Television
 Through local NGO or other local contact	 Departmental/Center research boards	 Newspaper
 Table set-up / in-person recruitment of public	 Snowball sampling	
 Classroom recruitment	 Social Media (Twitter/Facebook):	
 Other:		

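### The protocol gives the village-level intervention two durations, four weeks and 12 weeks, and expects analysis to finish before the week-12 primary outcome exists

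*Protocol*

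**What the plan says.** **Duration in the research plan.** Section IV, item 3, introduces the village-level package with "In the treatment arm we will conduct the following intervention activities for four weeks". The list that follows includes two recurring distributions:

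- at mosques: "Distribute one mask to each worshipper as he enters the mosque for Jummah prayer each Friday"
- at markets: "Every other day, distribute one mask to each person who visits the markets"

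It also has a door-to-door visit to "distribute up to 2 masks to each household", made right after the baseline survey.

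**Duration in the general information.** Section I, item 1, says "The main trial is expected to start on September 23" and that it lasts 12 weeks. It continues: "Throughout the 12 weeks of the study duration", dated September 23 to December 12, "we will conduct mask distribution and promotion as well as field observations of participants behavior". The sentence is not limited to one of the two experiments. Section V, item 1, adds "We will also hire monitors who will go around each market throughout the study period to encourage people to wear masks", which suits the longer period but gives no number of weeks.

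**Analysis date and primary outcome.** Section I, item 1, also expects all data analysis to be finished within November. The village-level primary outcome is symptomatic infection assessed by serology at 12 weeks (Section IV, Primary outcomes). The blood is drawn 12 weeks after the initial intervention (Section IV, Serology tests).

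**End dates.** Section VI, items 4 and 7, has identifiers destroyed after study completion, by January 2021.

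**The concern.** The same activities, mask distribution and promotion, are given two lengths that differ threefold. The length is part of the definition of the intervention. Under one reading, the primary comparison at week 12 tests a package that stopped about eight weeks earlier. Under the other, it tests a package delivered up to about the time the blood is drawn. The mask-use counts change meaning too: a count made after week 4 shows persistence once promotion has ended under the first reading, and use during active promotion under the second. A reader of the result would not know which of these the protocol had planned.

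The analysis date is a separate matter. If it were followed, the completed analysis would contain no week-12 serology, and so no primary outcome.

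**Working it through.** No sample size, power or event count is involved. The check is calendar arithmetic plus a comparison of the sections.

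**Inputs.** Start September 23, 2020, stated window to December 12, 2020, and November completion of analysis (Section I, item 1). Four weeks, every Friday, and every other day (Section IV, Intervention activities). Week-12 serology (Section IV, Primary outcomes and Serology tests). January 2021 for identifiers (Section VI, items 4 and 7). The November date carries no year. Since the study is to be complete by January 2021, it is read as November 2020.

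**The protocol's own figure.** September 23 to December 12 is 80 days, or 81 counted inclusively: 80/7 = 11.4 and 81/7 = 11.6 weeks. The 12 weeks is thus a rounded label, which is not a fault in itself.

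**Delivery under each reading.** This assumes that every village starts on September 23, which the protocol does not say. Days are counted inclusively.

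| | Four weeks (Sep 23 to Oct 20) | Stated window (Sep 23 to Dec 12) |
|---|---|---|
| Days | 28 | 81 |
| Friday mosque distributions | 4 (Sep 25, Oct 2, 9, 16) | 12 (Sep 25 to Dec 11) |
| Market distributions, every other day | 28/2 = 14 | 40 or 41 |
| Total sessions | 4 + 14 = 18 | 12 + 40 = 52, or 12 + 41 = 53 |

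The household visit happens once under either reading and is left out.

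**Analysis date against the primary outcome.**

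- Week 12 = September 23 + 84 days = December 16, 2020.
- November 30 is day 68 after the start: 68/7 = 9.7 weeks.
- December 16 − November 30 = 16 days. Even the stated study end, December 12, is 12 days after November 30. Neither gap allows any laboratory time.
- For week 12 to fall by November 30, the start would have to be no later than November 30 − 84 days = September 7, before the stated start.

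**Could a roll-out reconcile the two durations?** With 700 markets+ of about 250 households each (Section IV, Study Design), the in-person baseline is about 700 × 250 = 175,000 household visits, so a same-day start everywhere is unlikely. If January 2021 means the end of that month, a last village start of November 8 reaches week 12 on November 8 + 84 days = January 31, 2021, just inside the identifier date. If it means January 1, the last start that fits is October 9. A roll-out is therefore possible under the stated dates, but no window or last start date is given.

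**The case against.** The strongest reply is that Section I is a general project-duration entry, written as an expectation and covering the pilot and both experiments, while Section IV is the specific description of the treatment arm. Four weeks per village, started in turn, would satisfy both statements. The number of baseline visits makes such a roll-out likely. The randomised comparison is valid under either duration, and the November date corrects itself, because blood cannot be analysed before it is drawn.

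Most of this stands. A reader might infer that the protocol's other dates rule out a roll-out, since Section I gives one calendar week for each follow-up survey and ends the study on December 12. The documents do not support that. Some roll-out windows fit the identifier date, as shown above. The December 12 end already falls before week 12 with no roll-out at all, so it does not discriminate. The survey weeks are too loosely set to settle the matter. A reader might also take 18 against 52 to 53 sessions as the actual difference in exposure. Those counts depend on a common start date and are an illustration only.

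The reply does not supply the missing statement. Section I names distribution and promotion explicitly, so the 12 weeks cannot be read as observation only, and no section mentions a roll-out. A roll-out would also move some villages' week 12 beyond December 16, further past November.

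**Conclusion.** Both points hold, at the level of a should-fix.

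1. The protocol gives four weeks and 12 weeks for the same activities and does not reconcile them, so the exposure behind the week-12 primary comparison is not fixed. Staggered four-week courses may be intended; the documents neither state nor exclude this.
2. Analysis completed in November 2020 cannot include the primary outcome. Week 12 is December 16 at the earliest, 16 days after the end of November. This rests only on the stated September 23 start and on reading November as November 2020.

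A reader might go further and infer that the randomised comparison is biased, or that the effect on mask use or infection would change by some amount. The documents do not support either. Treatment and control are compared validly under either duration, and distributed masks and leaders' commitments may outlast the active period. What is missing is a clear statement of what the comparison tests.

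**What to change.** - Reconcile Section I, item 1, with Section IV, Intervention activities, so that the protocol states either one intervention duration, or a per-village duration with an explicit roll-out window and last start date. The sponsor must say which was meant; this review does not choose.
- Restate the expected analysis date so that the primary analysis follows the last village's week-12 serology.
- Check the study end date in Section I and the identifier-destruction date in Section VI, items 4 and 7, against the last village's week 12, and move them if needed.

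The cost is protocol wording and a later stated analysis date. Sample size and randomisation do not change. If a roll-out is stated, the end dates may also have to move.
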